10.6 Appendix 6: Renal safety monitoring

Once a participant is exposed to study treatment, the following two categories of abnormal renal laboratory alert values should be assessed during the study period:

- Serum creatinine increase $\geq 25\%$ compared to baseline during normal hydration status
- Any one of the following:
 - Urine protein-creatinine ratio (PCR) ≥ 1 g/g or ≥ 100 mg/mmol, OR
 - New onset dipstick proteinuria $\geq 3+$, OR
 - New onset dipstick hematuria $\geq 3+$ (after excluding menstruation, UTI, extreme exercise, or trauma)

Abnormal renal event findings must be confirmed within 24-48 hours after the first assessment.

Once a participant is exposed to study treatment, renal laboratory alerts or renal safety events should be monitored and followed up by the Investigator or designated trial staff as summarized in [Section 10.5](#).

10.6.1 Specific Renal Alert Criteria and Actions and Event Follow-up

Table 10-4 Specific renal alert criteria and actions

Renal Event	Actions
eGFR decrease 25-49%	
 • Consider causes and possible interventions • Repeat laboratory values within 48 hours of receipt of abnormal test results. Assess patient for signs and symptoms of illness, AKI, etc.
eGFR decrease $\geq 50\%$ * OR if <18 years old, eGFR < 35 mL/min/1.73 m ²	
 • Consider causes and possible interventions • Repeat assessment within 24-48 hours if possible • Repeat laboratory values within 48 hours of receipt of abnormal test results. Assess patient for signs and symptoms of illness, AKI, etc. • Consider drug interruption or discontinuation unless other causes are diagnosed and corrected • Consider referral to nephrologist for diagnosis and management • Consider patient hospitalization and specialized treatment
New onset dipstick proteinuria $\geq 3+$ OR PCR ≥ 1 g/g Cr	
 • Confirm presence of true proteinuria by quantification: protein-creatinine on first morning void • Consider causes and possible interventions • Assess serum albumin & serum total protein

Renal Event	Actions
New onset hematuria \geq 3+ on urine dipstick	
 • Repeat assessment to confirm • Consider drug interruption or discontinuation unless other causes are diagnosed and corrected • Consider referral to a nephrologist • Obtain urine microscopy to distinguish hemoglobinuria or myoglobinuria from hematuria • Assess sCr • Exclude infection, trauma, calculi, bleeding from the distal urinary tract/bladder, menstruation • Consider bleeding disorder

* Corresponds to KDIGO criteria for Acute Kidney Injury

Table 10-5 Renal Event Follow-Up

FOLLOW-UP OF RENAL EVENTS

Monitor patient regularly (frequency dependent on clinical course and consultant advisement) until -

- Event resolution: sCr within 10% of baseline or PCR < 1 g/g Cr, or ACR <300 mg/g Cr, or
- Event stabilization: sCr level with \pm 10% variability over last 6 months or PCR stabilization at a new level with \pm 50% variability over last 6 months.

Analysis of urine renal markers in samples collected over the course of the DIN event

11 References

References are available upon request

TET2	Tet methylcytosine dioxygenase 2 gene
TFL	Tables, Figures, Listings
VAF	Variant allele frequency
vWF	Von Willebrand Factor
WLIMS	Watson Laboratory Information Management System

1 Introduction

This statistical analysis plan (SAP) describes all planned analyses for the Clinical Study Report (CSR) of study CADPT15A12201, a randomized, placebo-controlled, parallel-group, investigator- and participant-blinded Phase 2a study to investigate the efficacy, safety, and tolerability of DFV890 and MAS825 for inflammatory marker reduction in adult participants with coronary heart disease and Clonal Hematopoiesis of Indeterminate Potential (CHIP).

The content of this SAP is based on protocol version 00 dated 28-Jul-2023 and Case Report Form (CRF) version 1.0 dated 09-Nov-2023.

Tables, Figures, Listings (TFL) details the presentation of the data, including shells of summary tables, figures and listings, and Programming Datasets Specification (PDS) contains programming specifications e.g. for derived variables and derived datasets, to support the creation of CSR and potential Interim Analysis (IA) outputs.

1.1 Study design

[figure not shown]
This is a multi-center, randomized, placebo-controlled, participant- and investigator-blinded study to evaluate the efficacy, safety, and tolerability of intra-individual dose escalation of DFV890 or a single s.c. dose of MAS825 for inflammatory marker reduction in participants with coronary heart disease and *TET2* or *DNMT3A* CHIP (VAF $\geq 2\%$). The study consists of a screening period up to 30 days; a treatment period of approximately 12 weeks with an end of treatment (EOT) visit on Day 85, which is one day after the last dose of DFV890 or placebo; a follow-up period of approximately 1 week; and a standard safety follow-up call approximately 30 days following the last dose. The overall study duration is approximately 21 weeks.

Approximately 28 participants will be randomized into the trial, of which a minimum of approximately 40% of randomized participants will be CHIP with *TET2* somatic mutations. For subgroup allocation, patients with *TET2* or *DNMT3A* CHIP will be determined based on their most common mutation (e.g., patients with mutations in both *DNMT3A* + *TET2* will be allocated to the subgroup based on the mutation with the highest VAF). Blood samples collected for CHIP genotyping on Day 1 and at the EOT visit will be analyzed at a central laboratory at EOS to explore changes in VAF, and will not be used for eligibility or subgroup allocation purposes.

Participants meeting all eligibility criteria will be randomized in a 4:4:4:1:1 ratio to one of the five treatment sequences as shown in [Figure 1-1](#) (1 MAS825+placebo sequence, 3 DFV890+placebo sequences, and 1 placebo-only sequence). Within each DFV890+placebo sequence, participants will start on either oral placebo or DFV890 10 mg QD.

On Day 1, participants will receive the first oral dose of DFV890 or placebo and the single s.c. dose of either MAS825 or placebo. None of the treatment sequences include a combination of both active DFV890 and active MAS825. After initial dosing, assessments will be conducted at site. Participants will then be provided with a sufficient amount of DFV890/DFV890 placebo doses for daily dosing until their next scheduled visit.

Figure 1-1 Study design

If applicable, the dose of DFV890 will be uptitrated (according to the specific treatment sequence to which the participant is assigned) approximately every three weeks at the scheduled visits on Days 22, 43 and 64 as shown in the study design figure. At these visits, efficacy, safety and tolerability assessments will be performed. Participants will take oral daily doses of DFV890 or placebo for a total of approximately 12 weeks. Participants will return for an EOT period visit on Day 85.

After the EOT visit, participants will return approximately 1 week later on Day 92 for an End of Study (EOS) visit.

1.2 Study objectives, endpoints and estimands

Table 1-1 Objectives and related endpoints

Objective(s)	Endpoint(s)
Primary objective(s)	Endpoint(s) for primary objective(s)

 To evaluate the effect of various dose levels of DFV890 versus placebo to reduce circulating levels of inflammatory markers in participants with coronary heart disease and CHIP To evaluate the effect of MAS825 versus placebo to reduce circulating levels of inflammatory markers in participants with coronary heart disease and CHIP 	
 Serum levels of IL-6 and IL-18 at 3 weeks after the start of a DFV890 dosing period Serum level of IL-6 at 3 weeks after a single s.c. dose of MAS825
Secondary objective(s)	Endpoint(s) for secondary objective(s)

 To evaluate the safety and tolerability of DFV890 and MAS825 in participants with coronary heart disease and CHIP To assess the PK of DFV890 in participants with coronary heart disease and CHIP To assess the PK of MAS825 in participants with coronary heart disease and CHIP 	
 Adverse events, and parameters from safety assessments, including vital signs, electrocardiograms (ECGs), and laboratory assessments (urine and blood) Plasma trough concentrations (C_{trough}) of DFV890 at steady-state Serum concentrations of MAS825 after a single s.c. dose of MAS825

Objective(s)	Endpoint(s)
Exploratory objective(s)	Endpoint(s) for exploratory objective(s)

 To assess the PK of IBW042 a metabolite of DFV890 in plasma To explore whether individual variation in the CYP2C9 gene related to drug metabolism confer differential PK response to DFV890 To assess the effect of DFV890 and MAS825 on PD and inflammation-related, and CVD-related biomarkers (including PK/PD relationships) 	
 Plasma Ctrough of IBW042 at various dose levels of DFV890 Plasma Ctrough of DFV890 and its metabolite, IBW042, as well as CYP2C9 genotype PD and inflammation-related markers may include but are not limited to hsCRP, soluble ASC, total IL-1β, CXCL9, CXCL10, hslFN-γ, vWF, total count and percentage of myeloid/lymphoid cells in peripheral blood by flow cytometry, and total IL-18 (MAS825 only) CVD-related biomarkers may include but are not limited to lipid parameters DFV890 and MAS825 concentrations at or up to corresponding time point

1.2.1 Primary estimand(s)

The primary clinical question of interest is: What is the effect of DFV890 and MAS825 in addition to SoC CVD prevention medication in patients with known coronary heart disease and presence of CHIP on the inflammatory markers IL-6 and IL-18 (IL-18 applicable for DFV890 only), assuming patients continue treatment with reasonable adherence and there are no new major cardiovascular events, initiations of prohibited medication, or febrile infections, but without regard to changes in SoC CVD prevention medication.

The justification for the estimand is that it will capture the effect of the investigational treatments versus placebo under research-like conditions, where participants adhere to their assigned treatment regimen and there is no impact of other intercurrent events on the primary endpoints (aside from potential changes in SoC CVD prevention medication).

The estimand is defined by the following attributes:

- Population: participants with known coronary heart disease and *TET2* or *DNMT3A* CHIP (VAF $\geq 2\%$) and potential SoC CVD prevention medication
- Endpoints: Change from baseline (day 1) in log transformed Serum levels of IL-6 and IL-18 at 3 weeks after the start of a dosing period for DFV890 and serum level of IL-6 at Week 3 for MAS825
- Treatment of interest: MAS825 or placebo single dose, DFV890 QD or DFV890 placebo QD

4. Handling of intercurrent events: see [Table 1-2](#)
5. Summary measure: the model-based difference in variable means between treatments.

Table 1-2 Intercurrent events for the primary estimand

Intercurrent event	Details (if necessary)	Handling of event
Permanent discontinuation of study treatment (DFV890 only)	Potential data collected during an EOT visit will be only used if collected within 1 day from the last dose and if the treatment duration is of at least 17 days in the dosing session affected.	Data collected after this intercurrent event will not be used for this estimand and set to missing
Incidence of a new major CVD event (e.g., myocardial infarction, stroke, etc.)	-	Data collected after this intercurrent event will not be used for this estimand and set to missing
Change in SoC CVD prevention medication	-	All data collected after this intercurrent event will be used for this estimand
Initiation of a prohibited medication for a comorbid condition	Unforeseen use of any medication expected to have a sustained effect on the primary endpoints (i.e., any systemic corticosteroids)	Data collected after this intercurrent event will not be used for this estimand and set to missing
	Unforeseen use of medication expected to have a limited effect on the primary endpoints (i.e., any other prohibited medications)	Only the assessment immediately following the event will be excluded for the purpose of this estimand and set to missing
New-onset febrile infection	Febrile infection around time of assessment classified as protocol deviation OTH02.	Only the assessment immediately following the event will be excluded for the purpose of this estimand and set to missing
Nonadherence to study treatment (DFV890 only)	Greater than 20% of missed daily doses within 3 weeks prior to an assessment or a treatment duration < 17 days	Only the assessment immediately following the event will be excluded for the purpose of this estimand and set to missing
	Any missed dose within the 2 days prior to an assessment	Only the assessment immediately following the event will be excluded for the purpose of this estimand and set to missing

The handling of each intercurrent event specified in [Table 1-2](#), with the exception of changes in SoC CVD prevention medication, reflects what is referred to as the hypothetical strategy, which aims to mimic a scenario in which the intercurrent event did not actually occur and all participants had adhered to the randomized treatment throughout the course of the study. To enable this strategy, data from various assessments taking place after the event will be excluded from the primary analysis, as described in the table. The exception to this is changes to SoC CVD prevention medication, which will be handled by a treatment policy strategy, in which any occurrence of the event is ignored and the subsequent data are included in the analysis.

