9. History of lymphoproliferative disease or any known malignancy or history of malignancy of any organ system within the past 5 years of the start of screening (except for basal cell carcinoma or actinic keratoses that have been treated with no evidence of recurrence in the past 3 months, or carcinoma in situ of the cervix or non-invasive malignant colon polyps that have been removed).
10. At screening, pre-malignant clonal cytopenias or clonal cytopenia of unknown significance (CCUS). Cytopenia in the context of clonal abnormalities is defined as an acquired and persistent anemia (hemoglobin < 12 g/dL in females and < 13 g/dL in males), neutropenia (ANC < $1.8 \times 10^9/L$), and/or thrombocytopenia (platelets < $150 \times 10^9/L$) that is not explained by another known or identifiable condition.
11. History of ongoing, chronic, or major recurrent infectious disease, at the discretion of the Investigator, at the start of screening.
12. Live vaccinations within 1 month prior to Day 1 or live vaccinations planned during the trial.
13. Patients with suspected or proven immunocompromised state at screening, including:
 - (a) known clinical diagnosis of Human Immunodeficiency Virus (HIV) infection. Patients on systemic anti-retroviral therapy are also excluded from the trial;
 - (b) those with any other medical condition which in the opinion of the Investigator places the patient at unacceptable risk for participation in immunomodulatory therapy
 - or (c) those requiring systemic or local treatment with any immune modulating agent in doses with systemic effects, e.g., high dose oral or i.v. steroids (>20 mg prednisone orally daily for >14 days, >5 mg prednisone orally daily or equivalent dose of i.v. steroid) or high dose methotrexate (>15 mg weekly). Topical, inhaled, local steroid use in doses that are not considered to cause systemic effects are permitted.
14. Use of any biologic drugs targeting the immune system (for example, but not limited to: tumour necrosis factor (TNF) blockers, anakinra, rituximab, abatacept, tocilizumab, or canakinumab) within 26 weeks of Day 1. Refer to [Section 6.8.2](#).
15. Known diagnosis of a systemic auto-immune disease (e.g., systemic lupus erythematosus, etc.).
16. Current use or within 5 half-lives of use of colchicine at start of screening.
17. Participants with a MI resulting from percutaneous coronary interventions (PCI) or coronary artery bypass graft (CABG) procedures.

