² The effect of grapefruit juice varies widely among brands and is concentration-, dose-, and preparation-dependent. Studies have shown that it can be classified as a “strong CYP3A inhibitor” when a certain preparation was used (e.g., high dose, double strength) or as a “moderate CYP3A inhibitor” when another preparation was used (e.g., low dose, single strength).

³ Herbal product

Table 6-7 Prohibited medication

Medication	Prohibition period	Action taken
Inhibitors and inducers of CYP3A or CYP2C9 according to Table 6-6	5 half-lives or 1 week (whichever is longer) prior to Day 1 through EOS	Discontinue study treatment
Other investigational drugs	Within 5 half-lives of Day 1 through EOS	Discontinue study treatment

Medication	Prohibition period	Action taken
Systemic or local treatment with any immune modulating agent in doses with systemic effects	4 weeks prior to Day 1 through EOS	Discontinue study treatment
Biologic drugs targeting the immune system	26 weeks prior to Day 1 until EOS	Discontinue study treatment
Colchicine	Within 5 half lives of the time of screening through EOS	Discontinue study treatment
Live vaccinations	4 weeks prior to Day 1 through EOS	Discontinue study treatment

7 Discontinuation of study treatment and participant discontinuation/withdrawal

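### Immune-targeting biologics sit in the limited-effect intercurrent-event row, so later IL-6/IL-18 values are kept whenever study treatment is not permanently stopped, and possibly in the MAS825 sequence

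*SAP*

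**What the plan says.** SAP 1.2.1, Table 1-2 splits prohibited medication into two rows, as does protocol 3.1, Table 3-2.

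- The sustained-effect row is "Unforeseen use of any medication expected to have a sustained effect on the primary endpoints (i.e., any systemic corticosteroids". All later data are discarded.
- The limited-effect row is "Unforeseen use of medication expected to have a limited effect on the primary endpoints (i.e., any other prohibited medications". Here "Only the assessment immediately following the event will be excluded for the purpose of this estimand and set to missing".

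Protocol 6.8.2, Table 6-7 lists what is prohibited. For immune-targeting biologics the period is "26 weeks prior to Day 1 until EOS". Exclusion criterion 14 in protocol 5.2 gives examples: "anakinra, rituximab, abatacept, tocilizumab, or canakinumab) within 26 weeks of Day 1". For immune-modulating agents at systemic doses the period is "4 weeks prior to Day 1 through EOS". The action column of Table 6-7 says in every row that study treatment is to be stopped, and protocol 7.1 lists use of prohibited treatment among the reasons for required discontinuation.

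Discontinuation is an intercurrent event of its own, after which later data are not used. In the SAP that row is headed "Permanent discontinuation of study treatment (DFV890 only"; the protocol's row carries no such limit.

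**The concern.** The estimand follows a hypothetical strategy: the effect as it would have been had no prohibited medication been started. A rule that drops one value and keeps the rest serves that aim only if the drug's effect has gone by the following visit. For antibodies against the cytokine pathway under study, the documents point the other way. A value kept while such a drug is acting would be attributed to DFV890, placebo or MAS825.

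The split is also inconsistent within itself. Systemic-dose steroids are the protocol's own example of a systemic immune modulator (criterion 13), so they share a Table 6-7 row with the other agents of that kind. Yet only steroids were given the sustained-effect handling.

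**Working it through.** The plan states no figure to reproduce here. The check is a reading of the tables, a count of visits and a rough size.

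**1. Which row applies.** Both rows define their content with i.e., which read literally closes the lists. A biologic is prohibited and is not a corticosteroid, so it falls in the limited-effect row.

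**2. Does limited effect fit the documents?**
- Required biologic-free time before Day 1: 26 × 7 = 182 days. Day 1 to Day 85 is 84 days.
- Protocol 8.3.3: canakinumab, one of the biologics named in criterion 14, lowered IL-6 from baseline by about 35% and 45% at about 3 months, when given every 3 months.
- SAP 2.1.1.2: one dose of MAS825, itself a cytokine antibody, is expected to act through the 12-week treatment period.

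**3. Values kept after a biologic under the limited-effect rule** (nominal visits on Days 22, 43, 64 and 85):

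| Start of biologic | Dropped | Kept | Kept values within 182 days |
|---|---|---|---|
| Days 1-21 | Day 22 | Days 43, 64, 85 | 3 of 3 |
| Days 22-42 | Day 43 | Days 64, 85 | 2 of 2 |
| Days 43-63 | Day 64 | Day 85 | 1 of 1 |
| Days 64-84 | Day 85 | none | none |

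Under the sustained-effect rule every count of kept values is 0.

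**4. Other systemic immune modulators (28 days).** The first kept value comes 21 days after the dropped visit. After a single use it lies within 28 days only if use was at most 7 days before the dropped visit: Days 15-21, 36-42 or 57-63. Continued use widens this, because the rule is tied to starting the drug.

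**5. When the limited-effect row decides anything.**
- *Sequences 2-5, Table 6-7 followed:* treatment stops permanently and the discontinuation row removes later values.
- *Sequences 2-5, treatment not permanently stopped:* protocol 6.8.2 says use may lead to withdrawal or to DFV890 being held, although 6.5 permits no interruptions. A hold is not permanent discontinuation, so the limited-effect row governs.
- *Sequence 1:* SAP Table 1-2 confines discontinuation to DFV890. SAP 2.1.1.11, Table 2-1 has no such limit and keeps visits more than 1 day after the last dose out of the Emax and traditional models. The two tables disagree. The values at stake are MAS825 Weeks 6, 9 and 12, which enter Model 5 for IL-6 (SAP 2.5.2). A biologic started before Day 22 removes the Week 3 value, and one started later cannot affect it.

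**6. Size.** Assume one affected participant, a canakinumab-like reduction r of 0.35 to 0.45, and unadjusted means. The log shift is k × ln(1 − r)/N, and the relative move is 1 − exp(shift). ln(0.65) = −0.431 and ln(0.55) = −0.598.

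| Group | k/N | Log shift | Move |
|---|---|---|---|
| 100 mg (8 + 8 + 2) | 1/18 | −0.024 to −0.033 | 2.4% to 3.3% |
| Pooled placebo (8 + 8 + 2 × 4 sessions) | 3/24 | −0.054 to −0.075 | 5.2% to 7.2% |
| One late MAS825 week | 1/8 | −0.054 to −0.075 | 5.2% to 7.2% |

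The 24 placebo sessions agree with SAP 2.4.1. The placebo row needs a Sequence 5 participant who starts a biologic in Dosing Period 1 and stays on tablets. Contamination at 100 mg exaggerates the DFV890 effect; contamination of placebo masks it.

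**The case against.** The strongest reply is that the protocol already deals with this. Table 6-7 stops study treatment for every prohibited class, 7.1 makes that mandatory, and the discontinuation row then discards the later data. For Sequences 2-5 this stands when the rule is followed. A reader who stops at the limited-effect row might infer that a biologic always costs just one value; the documents do not support that. But if treatment were always stopped, the limited-effect row would have no work to do in those sequences. It operates only where treatment continues, which is where the kept values are affected.

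Other replies, and what remains of them:

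- *The hold in 6.8.2 is aimed at drug interactions and limited need.* Its context suggests so, but its last sentence covers any prohibited concomitant medication. A hold may also trigger the nonadherence rows, which again remove only the next assessment.
- *Deviation review is a second safeguard.* SAP 2.2 has that review take Table 1-2 into account, and the relevant codes in SAP Table 5-4 act on the corresponding treatment period.
- *The i.e. is loose drafting.* Possibly, since the documents use i.e. and e.g. interchangeably elsewhere. Row membership is then undefined, and the same edit is needed.
- *Raw means are not the estimator.* Correct. The Emax model has a participant random effect on E0, and Model 5 a random intercept. Either would absorb part of a shift that persists across visits.

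Four further inferences should be resisted. Twenty-six weeks is a prohibition period, not a stated duration of action. The MAS825 Week 3 value is not exposed. For colchicine the documents give only a number of half-lives, with no half-life and no effect on IL-6 or IL-18, so they do not show that it belongs in the sustained-effect row. Nor do they support an IL-6 shift larger than 35% to 45%.

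**Conclusion.** The point holds in a limited form. Placing immune-targeting biologics in the limited-effect row does not fit the protocol's 26-week prohibition or its own canakinumab evidence, and it works against the hypothetical strategy. The fault is in protocol Table 3-2 and is carried into the SAP.

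It has consequences only where oral treatment is held or continued after a biologic, and possibly in Sequence 1, where SAP Tables 1-2 and 2-1 disagree and the late MAS825 IL-6 values in Model 5 are affected. One such participant would move a group mean by roughly 2% to 7%. That rests on a canakinumab-like reduction and unadjusted means. The documents give no event frequency; with autoimmune disease and need for systemic immune modulators excluded at entry, the event should be rare. The case for systemic immune modulators other than biologics is weaker, resting on a 28-day prohibition against a 21-day visit interval. A correction is worthwhile because it is cheap and the groups are small, not because a large bias is expected.

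**What to change.** In protocol Table 3-2 and SAP Table 1-2:

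1. Define the sustained-effect row as systemic corticosteroids, biologics targeting the immune system, and other immune-modulating agents at systemic doses. Apply it to all sequences, with all later IL-6/IL-18 values set to missing.
2. In the limited-effect row, exclude every assessment made while the drug is still being taken, not only the first.
3. State which row takes precedence when prohibited medication leads to discontinuation.
4. Align SAP Table 1-2 with SAP Table 2-1 on what discontinuation means in Sequence 1.

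Separately, the protocol passages on stopping or holding treatment (6.5, 6.8.2, Table 6-7 and 7.1) must be reconciled. Which clinical rule should apply is for the sponsor to settle; the estimand rows should then match it.

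The cost is wording in two tables and, at most, a few more missing values in a rare event.
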